4. STATISTICAL CONSIDERATIONS

Number of subjects

Strength calculation is not required for pilot studies for Phase III trials and is in some cases even advised against (Billingham et al., 2013; Thabane et al., 2010). Based on comparable feasibility studies on testing new treatment methods for clients with PTSD (Mahoney et al., 2020; Scharff et al., 2020), we have estimated that 30 participants in the intervention and 30 in the control group are required for a representative sample.

Statistical analysis

Data from this pilot study will help provide information for a future efficacy RCT (Phase III trial) by testing the trial procedures. Therefore, no formal statistical analysis of data from the pilot study will be carried out. A description of the participants and a simple compiling of pilot data will be presented. Exploratory analyses will be conducted to compare means (and 95% confidence intervals) of the ITQ and the other secondary outcome measures between intervention and control group at the end of the treatment using a t-test. Furthermore, repeated measurements within the same group will be analysed using variance analysis (ANOVA). All randomised participants will be included in the analyses. The statistical analyses of pilot data will only be exploratory since the sample size does not allow for definitive analyses.

We will consider the study as complete if the following success criteria are met:

1. > 70% of potential participants accept and be included in the study

2. Completion rate of 70%, that is, we expect to have complete data (Measurement 4, completed at the final therapy session) of at least 70% of all participants included
3. Complete three-month follow-up (Measurement 5, obtained via e-Box) of at least 50% of all participants included

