1. Assess changes in symptoms of complex PTSD, assessed with the International Trauma Questionnaire (ITQ; Cloitre et al., 2018) between the intervention and control group as well as within each group
2. Examine changes in levels of comorbidity associated with CPTSD, such as anxiety, depression, insomnia, somatic complaints, drugs and alcohol intake between the intervention and control group as well as within each group
3. Examine changes in well-being, functioning and attachment style between the intervention and control group as well as within each group
4. Examine developments in client motivation and working alliance between the intervention and control group as well as within each group

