As an integral part of the treatment, a short assessment is conducted after each treatment module by having the client complete the primary outcome measure, the International Trauma Questionnaire (ITQ; Cloitre et al., 2018), which is used as a measure for assessing ICD-11 PTSD and CPTSD. In practice, the client fills in the ITQ on a tablet in the beginning of the last session of each treatment module, after which the client and therapist receive an automatic response on the tablet, establishing whether the client (based on the ITQ) continues to meet the diagnostic criteria for PTSD or CPTSD. If the client has achieved sufficient symptom recovery and no longer meets the diagnostic criteria for CPTSD, the client is considered a treatment completer. However, the client and the therapist might decide to continue treatment until the client no longer meets the diagnostic criteria for PTSD. In this way, treatment can continue up till 32 therapy sessions but client and therapist can end the treatment earlier if the client has a valid assessment and falls out of CPTSD criteria.

After completing the MPC treatment, the client cannot receive psychological treatment at the Danish Veteran Centre, until a three-month follow-up of the treatment effect has been completed. However, after a three-month follow-up, the client is welcome to seek psychological treatment again at the Danish Veteran Centre. If deemed relevant, the client is offered help and support from the Counselling and Rehabilitation Department as well as from the Family Unit under the Danish Veteran Centre, independently of the MPC treatment programme. If a client is assessed to require psychological treatment before the three-month follow-up, this will be initiated. As part of the three-month follow-up, all clients respond to whether they have received other help and support from the Danish Veteran Centre or others after ending their MPC treatment.

Practical implementation

Treatment sites and participating therapists (will be updated regularly)

The treatment is carried out at five local veteran centres in Denmark by six clinical psychologists employed by the MPD, Danish Veteran Centre:

1. [name]. Clinical psychologists: [name] and [name].
2. [name]. Clinical psychologist: [name]
3. [name]. Clinical psychologist: [name]

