4. [name]. Clinical psychologist: [name]
5. [name]. Clinical psychologist: [name]

The treatment is carried out by clinical psychologists who have either helped develop the treatment programme or have received training and regular method-specific supervision in the MPC treatment programme. The six participating psychologists have different levels of experience. The four of them are authorised and specialists in psychotraumatology or psychotherapy for adults, one is authorised and one is about to be authorised.

Referral procedure

For veterans who are seeking psychological treatment at the MPD, the Danish Veteran Centre, and who are potentially offered to participate in the research project, the referral procedure is as follows:

1. ***1st measurement, 'Baseline'***. When a veteran seeking treatment contacts the MPD for psychological treatment, they are invited to a visitation interview as part of the regular procedure. Prior to the interview, the veteran receives a package of questionnaires in their digital mailbox (e-Boks) as part of the regular procedure at the MPD. The questionnaires of the 1st measurement ('Baseline') are presented in Table 2 and are described in more detail below ('Evaluation and Effect Analysis').
2. ***Visitation interview***. Prior to the visitation interview, the assessing psychologist receives a short report that provides an inventory of most questionnaires from the 1st measurement. Among other things, the assessing psychologist receives an inventory of the client's response

to the ITQ. If the veteran meets the diagnostic criteria for CPTSD, based on the results of the ITQ, and if the assessing psychologist deems MPC to be a relevant treatment offer, the assessing psychologist will inform the veteran of the research project. If the client is interested in hearing more about the project, they are invited to an initial interview with the treating psychologist.

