The treatment is registered in COSMIC (the record keeping system used at the MPD). Treatment record is used for treatment sessions, and the treatment ends with a concluding record.

Supervision

The participating therapists receive method-specific supervision in MPC every 14 days by supervisors [name] and [name], who have been involved in the development of the treatment programme. In addition, all therapists receive supervision in Trauma-Focused Cognitive Behavioral Therapy on a monthly basis, as part of the regular routine at the MPD.

Evaluation of treatment effects

A thorough effect evaluation of the MPC treatment programme will be carried out with questionnaires completed by the clients before, during and after the treatment. In addition, the therapeutic process will be evaluated with questionnaires completed by the client after each treatment module.

Table 2 provides an overview of all measurement times and questionnaires used for the process and outcome assessment of the MPC treatment programme.

Questionnaires	Num- ber of items	Time of admin- istration (minutes)	Measurement times				
			Before treatment 1st measurement 'Baseline' (package of question- naire is sent to the cli- ent's e-Boks as part of the regular procedure at the MPD)	During treatment 2nd measurement 'Beginning of treat- ment' Questionnaire package is completed on tablet before randomisation and first therapy ses- sion	3rd measurement 'Continuous process and effect evaluation' ^a Four questionnaires are completed after each treat- ment module	After treatment 4th measurement 'End of treatment' Questionnaire package is completed on tablet after last therapy session	3-month follow-up 5th measurement '3-month follow-up' (questionnaire package is sent to the client's e-Boks)
Demographic in- formation	5	2:23	X			X	X
Suicidal thoughts and behaviour	4	0:35	X			X	X
Prior treatment	7	0:52	X				
Medicine	2	0:22				X	X
TLEQ	23	7:33	X			X	X
DASS-42	42	2:50	X			X	X
ITQ	20	2:49	X	X	X	X	X
PCL-C	17	1:49	X			X	X
ADRS	6	0:48	X				
Alcohol intake	3	1:02	X			X	X
Drugs	7	0:49	X			X	X
WHO-5	5	1:02	X	X		X	X
SDS	3	1:01	X	X		X	X
ACE	25	5:40		X			
ISI	7	1:40		X		X	X
CMDQ	12	2:58		X		X	X
ECR-S	12	2:24		X		X	X
Social support	12	2:20		X		X	X
Other help and support	10	2:00				X	X
CMTS	24	2:38			X		
SAI	6	0:44			X		

Number of items	142	106	57	237	184
Estimated use of time (minutes)	24	20	7	30	34

Table 2. Overview of measurement times and questionnaires

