5. TARGET GROUP/PARTICIPANTS

During the recruitment period, all veterans who turn to the MPD with CPTSD will be invited to participate in the study. Clients are selected to participate on the following in- and exclusion criteria:

Inclusion criteria

- Meets the diagnostic criteria for CPTSD, assessed with the ITQ
- Danish veteran (cf. the Veteran Policy of Denmark³)
- Seeks help for deployment-related psychological issues

Exclusion criteria

- Severely suicidal⁴
- Current alcohol or drug abuse that prevents treatment⁵
- Blast injuries or current severe attention disorder
- Has received psychotherapeutic treatment in the past three months
- Is participating in another research project⁶ that interferes with this research project

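### The only between-arm analysis is an unadjusted end-of-treatment t-test, although pre-randomisation scores on the same scales are collected; with 42 completers, adjusting for them narrows the expected 95% CI once the pre-post correlation exceeds about 0.17

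*Combined protocol and SAP*

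**What the plan says.** Section 4 (Statistical analysis) plans an exploratory comparison of means, with 95% confidence intervals, for the ITQ and the secondary outcomes "between intervention and control group at the end of the treatment using a t-test". The only other analysis is a repeated-measures ANOVA within each group, which does not adjust the between-arm contrast. No section names a baseline covariate or a change score for that contrast.

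The earlier scores exist. In Table 2 (section 3) the 2nd measurement covers the ITQ, WHO-5, SDS, ISI, CMDQ and ECR-S, and "Questionnaire package is completed on tablet before randomisation". DASS-42 and PCL-C are taken at the 1st measurement, which under Referral procedure is sent out ahead of the visitation interview. All eight scales are repeated at the end of treatment.

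The between-arm comparison serves secondary objectives framed as change. Objective 1 is to "Assess changes in symptoms of complex PTSD, assessed with the International Trauma Questionnaire" between and within groups, and objective 3 is to "Examine changes in well-being, functioning and attachment style between the intervention and control group as well as within each group".

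**The concern.** Under randomisation, the difference in end-of-treatment means and the difference in mean change have the same expectation. The t-test therefore estimates the right quantity. What it discards is the information in the participant's own earlier score, which has two consequences:

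- The residual variance includes variation that the earlier score could explain, so the interval is wider than it needs to be when the pre-post correlation r is more than small.
- Any chance difference between the arms before treatment passes into the estimate. In standardised units the share carried over is r; in raw scores it is r multiplied by the ratio of the end SD to the pre-randomisation SD.

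The t-test is the only between-arm analysis described, so its differences and intervals are the plan's whole answer to the between-arm part of secondary objectives 1 to 3. The plan itself says the sample is too small for definitive analysis, which makes a nearly free gain in precision worth taking.

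**Working it through.** **Inputs from the documents.** 60 participants, 30 per arm (section 3, Randomisation); 95% intervals (section 4). Success criterion 2 reads "we expect to have complete data (Measurement 4, completed at the final therapy session) of at least 70% of all participants included", so 0.70 × 60 = 42. Section 4 gives no SD, effect size or power calculation, so there is no precision figure of the plan's own to reproduce.

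**Assumptions.** 21 completers per arm, a common SD, a linear relation between earlier and end score, and an approximately normal covariate. The documents do not give r, so a range is shown.

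**Half-width of the 95% CI, in SD units of the end score, n per arm**

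- t-test: t(0.975, 2n−2) × √(2/n)
- ANCOVA, one covariate: t(0.975, 2n−3) × √[(1−r²) × (2/n) × (1 + 1/(2n−4))]

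The factor 1 + 1/(2n−4) charges ANCOVA for the expected chance imbalance in the covariate; the lost degree of freedom is in the t quantile.

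**t-test**

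- n = 21: 2.0211 × √(2/21) = 0.624
- n = 30: 2.0017 × √(2/30) = 0.517

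**ANCOVA**

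| r (assumed) | 42 analysed | Change from 0.624 | Worth in extra participants (42) | 60 analysed | Simulated trials in which ANCOVA is narrower (42) |
|---|---|---|---|---|---|
| 0 | 0.632 | +1.4% | none | 0.522 | 20% |
| 0.2 | 0.620 | −0.7% | 1% | 0.511 | 48% |
| 0.3 | 0.603 | −3.3% | 7% | 0.498 | 71% |
| 0.5 | 0.548 | −12.2% | 30% | 0.452 | 97% |
| 0.7 | 0.452 | −27.6% | 91% | 0.373 | not simulated |

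The extra-participants column is the squared ratio of half-widths minus 1; at r = 0.5, (0.6237/0.5477)² = 1.297.

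**Break-even r.** Setting the two half-widths equal:

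- n = 21: r* = √[1 − (2.02108/2.02269)² × 38/39] = 0.165
- n = 30: r* = √[1 − (2.00172/2.00247)² × 56/57] = 0.135

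A simulation of 200,000 trials per value of r at n = 21 puts the crossing of mean widths between 0.160 and 0.165. An uneven split of the 42 leaves the break-even unchanged. In simulation both methods had type I error of 0.050 to 0.053.

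**Chance imbalance carried into the unadjusted estimate, n = 21.** The 95% range is ±1.96 × r × √(2/21) = ±0.12, ±0.18, ±0.30 or ±0.42 SD at r = 0.2, 0.3, 0.5 or 0.7.

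**How large might r be?** For the ITQ there is reason for caution. Entry requires that the client "Meets the diagnostic criteria for CPTSD, assessed with the ITQ", which restricts the range at the start. Under Treatment completion, "client and therapist can end the treatment earlier if the client has a valid assessment and falls out of CPTSD criteria", which ties the end score to the same scale. For DASS-42 and PCL-C the only earlier score is the 1st measurement, so the gap to the end of treatment is longer than for the other scales.

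**The case against.** The strongest reply is that the t-test is valid, the analysis is declared exploratory, the primary objectives concern process and resources, and no success criterion uses these estimates. All of that is true. It limits the importance of the point but gives no reason to keep the less precise method.

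Second, the gain depends on a correlation the documents do not supply, and the ITQ may have a low one. This stands as a limit on the claim: the gains at r = 0.5 and 0.7 are illustrations, not forecasts. The trade is still lopsided, with an expected loss of at most 1.4% against an interval 12% narrower at r = 0.5.

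Third, 0.17 is a threshold for expected width. At r = 0.165 the ANCOVA interval is the narrower one in only about 40% of trials with 42 completers, and at r = 0.2 in just under half. A benefit in most trials needs r nearer 0.3. That caution also stands.

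Fourth, section 4 says everyone randomised will be analysed, whereas 42 is the minimum of a feasibility criterion. Results for 60 are therefore given as well, and the conclusion is the same. Protection by randomisation does not carry over automatically to a completers-only comparison, and ANCOVA on complete cases does not cure that.

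**Conclusion.** The point holds as a recommended improvement, not as an error. The plan's one between-arm analysis leaves out scores it already collects. Adjusting for the single matching score narrows the expected interval when r exceeds about 0.17 with 42 analysed or about 0.14 with 60. At r = 0 the expected interval is 1.4% or 0.9% wider. These figures rest on equal arms, a common SD, a linear relation and a roughly normal covariate. The size of the gain is conditional on r, which the documents do not give. Feasibility conclusions are unaffected; only the width of the exploratory intervals and their exposure to chance baseline imbalance change.

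**What to change.** In section 4 (Statistical analysis), replace the t-test sentence, for continuous outcomes, with wording such as:

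> For each continuous outcome with a pre-randomisation score, the arms will be compared by ANCOVA of the end-of-treatment score on treatment arm and the participant's own pre-randomisation score: the 2nd measurement for ITQ, WHO-5, SDS, ISI, CMDQ and ECR-S, and the 1st for DASS-42 and PCL-C. The adjusted mean difference and its 95% CI will be reported as exploratory.

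Raw means by arm can still be shown alongside. The change does not cover the alcohol and drug items, which are frequency, quantity or yes/no responses, or CMTS and SAI, which are first collected after randomisation.

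The cost is one sentence and one degree of freedom, with no new data. A term for the stratification site is optional and should not be counted on for precision. Assuming five equal sites and 42 completers, it makes the expected interval about 3.4% wider than the t-test's at r = 0 with no site effect. The break-even r is then about 0.26, or about 0.16 if the site ICC is 0.05. The documents give no ICC, and the site list may change.

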3. METHODS

Study design

The study is a randomised controlled pilot study that follows the guidelines of the *Consolidated Standards of Reporting Trials* (CONSORT; Boutron et al., 2017) and the SPIRIT guidelines (Chan et al., 2013).

Randomisation

We wish to recruit 60 clients who will be randomised for the modular patient-centred CBT (MPC) or a control treatment, where the order of the treatment modules is determined in advance (described in more detail below). A randomisation list will be prepared using R software (www.r-project.org). Participants will be randomised into an intervention group (MPC) or a control group (MPC without co-decision) with 30 participants in each group, stratified by recruitment/treatment site. A block size of six will be used to ensure an even balance. The randomisation list will be prepared by a data manager affiliated with the project, and only he will be able to see the randomisation list. First, the assessing psychologist will complete the informed consent procedure, and then the therapist will perform the 2nd measurement ('Beginning of treatment', see Table 2 below) with the client (by having the client complete a questionnaire package on a small laptop with

pressure sensitive screen (tablet). The random allocation will then take place automatically on the tablet if the therapist determines that the client meets the inclusion criteria.

Intervention: Modular Patient Centred CBT for CPTSD

MPC (Folke, Friis, Thomsen & Roitmann, 2020) is a treatment programme consisting of up to 32 therapy sessions broken down by five treatment modules (each consisting of six sessions). Prior to the treatment modules, the client will complete an intro module (two sessions) focusing on psychoeducation on CPTSD, individual case formulation and introduction to the further treatment programme (including the content of the different modules). After the intro module (and after each treatment module), the client and therapist jointly decide which treatment module to proceed with based on 'co-decision', which is described in more detail in the manual. The order of the treatment modules is decided on the basis of a joint assessment of the client's most prominent symptoms, the client's preferences and wishes as well as the client's state of readiness to work with e.g. trauma processing.

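### Randomisation is stratified by site, but the exploratory between-arm t-test has no site term, so its 95% intervals are slightly too wide whenever sites differ

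*Combined protocol and SAP*

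**What the plan says.** The combined protocol and SAP, section 3 (Randomisation), plans 60 clients, 30 per arm, "stratified by recruitment/treatment site. A block size of six will be used to ensure an even balance". Under Treatment sites and participating therapists, "The treatment is carried out at five local veteran centres in Denmark by six clinical psychologists". The list shows two psychologists at the first site and one at each of the other four. The same section says "The six participating psychologists have different levels of experience": four are authorised specialists, one is authorised, and one is close to authorisation.

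Section 4 (Statistical analysis) compares the ITQ and the secondary outcomes "between intervention and control group at the end of the treatment using a t-test", reporting means and 95% confidence intervals. It mentions neither site nor therapist. It also says that no formal analysis will be done and that the comparisons are exploratory. Its three success criteria concern acceptance, end-of-treatment data from at least 70%, and three-month follow-up from at least 50%.

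**The concern.** When arms are balanced within site, a difference between sites adds about equally to both arm means and cancels from their difference. A two-sample t-test does not know this. It pools the spread within each arm, which includes the spread between sites, and so gives a standard error that is too large for a stratified design. The protocol's own account of therapist experience makes some difference between sites plausible.

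What is at stake is how precisely the arm difference is reported. Change in symptoms, comorbidity and functioning between groups is a secondary objective (section 2), and these intervals will be published.

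**Working it through.** **Inputs from the documents:** N = 60, 30 per arm; five sites; blocks of six; 95% intervals; at least 70% with end-of-treatment data (0.70 × 60 = 42). There is no power calculation to reproduce; 30 + 30 agrees with the stated 60.

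**Assumptions:** outcome SD 1; no true arm difference and the same arm effect at every site; site share of outcome variance (ICC, ρ) from 0 to 0.30; sites of 12 each, or 20/10/10/10/10. The interval examined is the one for the arm difference that goes with the t-test.

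**Closed form, 12 per site, all 60 analysed.** Each arm has six clients at each site.

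- True variance of the arm difference: (1 − ρ) × 2/30, because the site terms cancel.
- Expected pooled variance in the t-test: [58(1 − ρ) + 2 × 6 × 4 × ρ]/58 = (1 − ρ) + (48/58)ρ.
- t-test half-width: t(0.975, 58 df) × √(pooled variance × 2/30).
- Site-adjusted half-width: t(0.975, 54 df) × √((1 − ρ) × 2/30).

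At ρ = 0.10 the pooled variance is 0.9 + 0.0828 = 0.9828. The half-widths are 2.002 × √0.06552 = 0.512 and 2.005 × √0.06 = 0.491, a reduction of 4%. Coverage is from 6,000 simulated trials per setting (Monte Carlo standard error about 0.3 points).

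| ICC | t-test half-width | Adjusted half-width | Change | t-test coverage |
|---|---|---|---|---|
| 0 | 0.517 | 0.518 | 0% | 94.6% |
| 0.05 | 0.515 | 0.505 | −2% | 95.4% |
| 0.10 | 0.512 | 0.491 | −4% | 96.0% |
| 0.20 | 0.508 | 0.463 | −9% | 96.5% |
| 0.30 | 0.503 | 0.433 | −14% | 97.4% |

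Adjusted coverage stayed at 94.5-95.1%. With complete, equal blocks the two methods give the same point estimate; only the interval changes.

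**Simulation with 70% returned at random**, mean adjusted width divided by mean t-test width:

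| ICC | 12 per site | 20/10/10/10/10 | t-test coverage (two layouts) |
|---|---|---|---|
| 0 | 1.02 | 1.03 | 95.2%, 95.4% |
| 0.05 | 1.00 | 1.01 | 95.4%, 95.3% |
| 0.10 | 0.98 | 0.98 | 95.7%, 95.3% |
| 0.20 | 0.93 | 0.94 | 96.6%, 95.7% |
| 0.30 | 0.88 | 0.89 | 96.8%, 96.6% |

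A separate run of 8,000 trials per setting gave the same width ratios, with t-test coverage of 95.8-96.3% at ICC 0.10-0.20. Adjusted coverage here was 94.8-95.4%.

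**Uneven return.** If a share p₁ of the analysed intervention arm and p₀ of the analysed control arm come from a site that differs by δ from the others, the unadjusted difference shifts by (p₁ − p₀)δ. A site term removes this shift if the arm effect is common and return is unrelated to outcome within site and arm.

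**The case against.** The strongest reply is that this hardly matters. Even the sign of the benefit depends on an ICC that the documents do not give: at 70% return, adjustment costs about 2% at ICC 0 and gains only about 2% at 0.10. The error is in the cautious direction. The plan calls the comparison exploratory, its primary objectives are process and resources, and no success criterion uses the interval. Section 4 says the pilot informs Phase III by testing procedures; nothing commits the sponsor to planning from this interval. All of that stands, and it fixes the weight of the point.

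Three stronger readings are tempting, and the documents do not support them.

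- *The t-test inflates false positives.* Under a common arm effect it does the opposite. If the arm effect varied between therapists, the interval could be too narrow for inference beyond these six, but the plan gives no figure for that and it was not computed.
- *The analysis discards the balance created by randomisation.* The point estimate keeps that protection; only the interval fails to reflect it.
- *The comparison is defenceless against uneven return.* Chance unevenness is sampling noise already inside the t-test interval, as the coverage above shows. Bias needs systematic differences in return by arm across sites, which nothing in the plan suggests. Suppose one site returns 6/6 and 2/6 while the other four return 4/6 per arm, and that site differs by 0.5 SD. The shift is (6/22 − 2/18) × 0.5 = 0.162 × 0.5 = 0.08 SD, about one eighth of the t-test half-width of about 0.64 SD at 22 versus 18. That case has only 40/60 = 67% returned, below the plan's own 70% criterion, so it illustrates the mechanism and is not an expected size.

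**Conclusion.** The mismatch between stratified randomisation and an unstratified comparison is real. Under a common arm effect the t-test intervals are slightly too wide whenever sites differ, covering about 96% rather than 95% at a site ICC of 0.10-0.20. At 70% return the site-adjusted interval ranges from about 2% wider (ICC 0) through no change (about 0.05) to 6-7% narrower (0.20). These sizes rest on assumed ICCs, assumed site sizes and return at random. The list of sites and therapists is marked as subject to updating, so the count of single-psychologist sites describes the current text. This is a minor, cheap improvement; the trial's feasibility conclusions do not depend on it.

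**What to change.** In section 4, replace the t-test for the ITQ and the secondary outcomes with a linear model of the end-of-treatment score on arm and site. Site enters as a fixed factor with the levels used for stratification. Report the adjusted arm difference with its 95% CI, and keep the exploratory label.

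Using psychologist instead of site at the two-psychologist centre is optional. The treating psychologist is known before allocation (section 3, Referral procedure), so it is a legitimate covariate, but it is not a stratification factor and matching the analysis to the design does not require it.

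The cost is one sentence and four degrees of freedom (five with the optional psychologist term). At 70% return that is an interval about 2% wider if sites do not differ at all. No extra data, visits or clients are needed. The change is best made before outcomes are analysed.
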